U-500 regular insulin (U-500R) is a five-fold concentrated form of insulin (contains 500 units of insulin per mL) indicated to improve glycemic control in adults and children with diabetes mellitus requiring more than 200 units of insulin per day. It was first approved in 1994 by the United States Food and Drug Administration (FDA).^{12,13} To avoid dosing errors, it is currently available for administration through pens and vials with the dedicated U-500R syringe.¹⁴ U-500R has unique prandial/basal actions¹⁵ and thus can be used as insulin monotherapy. However, the safety and efficacy of U-500R used in combination with other insulins has not yet been determined. Also, the safety and efficacy of U-500R delivered by continuous subcutaneous infusion is been determined in a recent clinical study.¹⁶ An open-label trial evaluated transitioning from high-dose U-100 to U-500R and demonstrated that similar reduction in A1c could be achieved with twice or thrice-daily regimens of U-500R, which mitigate physical discomfort and potential barriers to adherence associated with U-100.¹¹ Measures of disease burden were reduced with both regimens while the compliance domain improved in patients receiving U-500R.¹⁷ In the real-world setting, U-500R (vial) has been shown to improve glycated hemoglobin (HbA1c) levels among patients with T2DM, **Error! Bookmark not defined.** and is associated with lower health care costs and better adherence than U-100 users prescribed a similar dose.^{17,18} A recent real-world study found that, U-500R Kwikpen initiation was associated with a clinically significant drop (~0.7% drop) in HbA1c accompanied by an average increase of 0.21 hypoglycemic event per year after adjusting for age, gender, race, BMI, CCI score, and TDD.¹⁹ The insulin dose increased more than 80 units/day on

[2019-8636] Observational Study Protocol

average after U-500R Kwikpen initiation and the medication adherence as measured by PDC improved.¹⁹

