Before U-500R use, the patients should be on basal-bolus regimen with more than one type of insulins. In contrast, U-500R is an insulin monotherapy. Because each type of insulin requires a copay at each refill, for the same amount of insulin purchased, it is likely more than one copay is required for basal-bolus regimen while only one copay is needed for U-500R. It is hypothesized that U-500R may have the potential to help reduce the out-of-pocket costs for patients while helping patients achieving their necessary insulin dose requirement. However, there is evidence that patients needed high dose insulin may be under-insulinized before switching to U-500R.^{15,19} These patients may have skipped a large amount of insulin as a result of avoiding injection pain or inconvenience due to large injection volume and multiple injections with multiple insulins. Under use is likely to lead to under purchase. Since the out-of-pocket costs would be dependent of the amount of insulin purchased, an artificially low out-of-pocket cost may be observed before U-500R initiation. In this study, we will examine the out-of-pocket costs together with other outcomes variables to understand whether this hypothesized scenarios played out in the real-world setting. We will further employ appropriate methodology to understand the factors that affect the out-of-pocket costs level and test whether the out-of-pocket costs differed before and after U-500R initiation after taking into consideration the factors that may affect the insulin purchasing behavior. In this study we will focus on out-of-pocket costs of those in the high-dose cohort. It is also interesting to see if the higher-dose cohort in this study may exhibit a different pattern of out-of-

[2019-8636] Observational Study Protocol

pocket costs from the lower-dose cohort in a parallel study. Please note that no statistical comparison will be made between the high-dose and the lower-dose cohorts as this is not the interest of the current study.

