5.3. Study Population

5.3.1 Selection Criteria

U-500R Syringe Initiators [Index Event a]

Inclusion Criteria

Patient will be included if they:

- had ≥ 1 prescription claim for U-500R vial during the identification period (VHA: 01JAN2014–30JUN2017; Truven: 01JUL2014–30JUN2017), with the first prescription claim for U-500R vial designated as index Event a (U-500R syringe initiation), and the date designated as the index date;
- had ≥ 2 claims with an ICD-9/10-CM code (Appendix 1) for T2DM in any position (primary/secondary) at any time prior to the index date;
- were aged ≥ 18 years on the index date;
- had continuous health plan enrollment with medical and pharmacy benefits for ≥ 9 months pre- and post-index event;
- had ≥ 1 prescription claim for any insulin other than U-500R in the pre-index period;
- had ≥ 1 HbA1c measurement within 90 days pre-index or 30 days post-index event;
- had ≥ 1 HbA1c measurement after the 30-day post-index period at any time in the 9-month post-index period;

[2019-8636] Observational Study Protocol

- had claims indicating TDD >180 in the post-index period;
- had claims indicating TDD >180 in the pre-index period; and

Exclusion Criteria

Patient will be excluded if they:

- had both T1DM and T2DM, had no oral anti-diabetic drug (OADs; Appendix 1) other than metformin, and the ratio between the number of T1DM and T2DM claims >0.5 at any time in the study period (VHA: 01APR2013–31MAR2018; Truven: 01JUL2013–30JUN2018);
- had previous use of U-500R in the 9-month pre-index period;
- had ≥ 1 claim with an ICD-9/10-CM code (Appendix 1) for secondary diabetes, gestational diabetes, diabetes complicating pregnancy, childbirth, puerperium, or non-clinical diabetes at any time during the 9-month pre-index period;
- had claims indicating pump use (Appendix 2) in the 9-month post-index (follow-up) period;
- had claims indicating TDD above 2000 units/day at any time in the pre-index or post-index periods; or
- had claims indicating insulin use other than U-500R in the post-index period.

U-500R Kwikpen Initiators [Index Event **b**]Inclusion Criteria

Patient will be included if they:

- had ≥ 1 prescription claim for U-500R Kwikpen administration during the identification period (VHA: 01JAN2014–30JUN2017; Truven: 01JUL2014–30JUN2017), with the first prescription claim for U-500R Kwikpen administration designated as Index Event **b**, and the date designated as the index date;

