[2019-8636] Observational Study Protocol

Variable	Source	Definition
Observed TDD in claims	Truven: Outpatient pharmacy claims table VHA: Pharmacy file	
The observed insulin TDD will be calculated as the total number of insulin units/total unique days of supply as recorded in claims and will be calculated both in the pre-and post-index periods among the high-dose U-500R Kwikpen initiators, high-dose U-500R syringe initiators, and any high-dose U-500R initiators. TDD will be reported as both a continuous and categorical variable.
 
For high-dose U-500R syringe initiators (Index Event a):
 
Total insulin units correspond to all the insulin units in pre-index and post-index periods, respectively.
 
For high-dose U-500R Kwikpen initiators (Index Event b):
 
Total insulin units correspond to all the insulin units in pre-index and post-index periods, respectively.
 
For any high-dose U-500R initiators (Index Event c):
 
Total insulin units correspond to all the insulin units in pre-index and post-index periods, respectively.
 
Note:
 
For the unique days supply in patients with evidence of a basal-bolus regimen, or basal/bolus-pre-mixed or basal/bolus-U-500R, the overlap days will be adjusted for the concomitant use of basal and bolus insulin products, but will not be adjusted within basal and within bolus insulins.

Change in observed TDD		The change in observed TDD will be defined as the difference between the pre- and post-index observed TDD.

[2019-8636] Observational Study Protocol

Variable	Source	Definition
Observed average daily dose (ADD) in claims	Truven: Outpatient pharmacy claims table VHA: Pharmacy file	
The observed insulin ADD will be calculated both in the pre-and post-index periods among the high-dose U-500R Kwikpen initiators, high-dose U-500R syringe initiators, and any high-dose U-500R initiators. ADD will be reported as both a continuous and categorical variable.
 
Pre-index ADD: the total number of insulin units/the total number of days in the pre-index period.
 
Post-index ADD: the total number of insulin units/ the total number of days in the post-index period
 
Note: Total insulin units calculation in based on the similar approach as described in TDD.

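### Observed TDD is not like for like across the index date: days with only one insulin class in supply dilute the pre-index dose, while U-500R refill gaps cancel

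*Protocol*

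**What the plan says.** Section 5.5, Table 2 defines observed TDD by a single formula for both periods: "The observed insulin TDD will be calculated as the total number of insulin units/total unique days of supply as recorded in claims". The numerator pools every product: "Total insulin units correspond to all the insulin units in pre-index and post-index periods, respectively". The note to the same row says that for mixed regimens "the overlap days will be adjusted for the concomitant use of basal and bolus insulin products", but that days "will not be adjusted within basal and within bolus insulins". The protocol does not define 'adjusted' further. Read with 'unique days', the natural meaning is that a day covered by both classes counts once, so the denominator is the union of supply days.

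The regimens differ by design. Section 3 expects combination therapy beforehand: "Before U-500R use, the patients should be on basal-bolus regimen with more than one type of insulins". Section 5.3.1 excludes patients who "had claims indicating insulin use other than U-500R in the post-index period".

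The same variable is the entry test ("had claims indicating TDD >180 in the pre-index period", with a matching post-index criterion) and the basis of the 2000 units/day exclusion. It is a Primary Objective 1 outcome, including its change. It is a time-varying covariate in the adherence, HbA1c, hypoglycemia and cost models of Section 6.4.1, and a mediator in the cost analysis. Table 2 also defines ADD, which divides by calendar days in both periods, but ADD is not used for entry, as a covariate or as a mediator.

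**The concern.** One formula behaves differently on the two sides of the index date. For a patient on two classes, measured TDD depends on how well the fills of the two classes line up. For a patient on U-500R alone it does not.

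Two things follow when neither dose nor refill behaviour has changed. First, the pre/post comparison shows a rise produced by the denominator. It points the same way as the suggestion in Section 3 that patients used too little insulin before switching, so it could be mistaken for support of it. Second, the >180 criterion asks for a higher dose on the claims before the index than after it, and it selectively removes multi-class patients whose fills are out of step. Because the distortion is aligned with the pre/post term, a larger sample does not reduce it.

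**Working it through.** **Inputs from the protocol.** The TDD formula, pooled numerator and overlap rule (Table 2); U-500R only after the index (Section 5.3.1); the >180 cut-off, which Section 3 justifies as 10% below 200 units/day; a VHA window of 9 months, taken as 270 days.

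**Inputs assumed.** The protocol does not give coverage per class, the basal/bolus split or how fills align. I use a constant 220 units/day (110 basal + 110 bolus, then 220 of U-500R) and show a range for coverage p.

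**The plan's own figure.** 200 × (1 − 0.10) = 180, as stated.

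**Step 1: worked example.** Each class covers 60 of every 90 days, so 180 of 270 days. Units = 2 × 110 × 180 = 39,600.
- Fills synchronised: 39,600 / 180 = 220.0.
- Bolus offset by 30 days, so the union is 270 days: 39,600 / 270 = 146.7.
- U-500R with the same gaps: 220 × 180 / 180 = 220.0.
- ADD: 39,600 / 270 = 146.7 in every case, before and after.

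The same purchases give a TDD change of 0 or of 220.0 − 146.7 = +73.3, depending only on fill alignment.

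**Step 2: general form.** For two equal classes with independent coverage p and claim dose D, units per calendar day are pD and the union share is 1 − (1 − p)² = p(2 − p). Hence pre-index TDD = D / (2 − p). For U-500R, TDD = pD / p = D. The false rise is D − D/(2 − p) = (1 − p) × measured pre-index TDD. The claim dose needed to measure 180 before the index is 180 × (2 − p).

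| p | 220 measured as | False rise, units/day | As % of measured | Claim dose needed to reach 180 pre-index |
|---|---|---|---|---|
| 0.95 | 209.5 | 10.5 | 5% | 189 |
| 0.90 | 200.0 | 20.0 | 10% | 198 |
| 0.80 | 183.3 | 36.7 | 20% | 216 |

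The post-index threshold stays at 180 throughout. At p = 0.9 the formula uses 18 of the 20 units allowed below 200, on the pre-index side only.

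**Step 3: fill-level simulation** (220 units/day, 30-day fills, random gaps, supply cut at day 270). Mean pre-index TDD was 198.6 at p = 0.91 and 181.0 at p = 0.80, against 220.0 after the index. The shares passing >180 before the index were about 100% and 56%, against 100% after it. Staggered fills with no gaps lost only days at the window edges: 215.8 with 30-day fills and 206.9 with 90-day fills.

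**Step 4: does the entry filter remove the bias?** No. Under the Step 2 assumptions, a two-class patient admitted with measured TDD above 180 carries a false rise above 180 × (1 − p): 9, 18 or 36 units/day at p = 0.95, 0.9 or 0.8.

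**Step 5: check of candidate fixes.**
- Per-class dose weighted by days in supply: (units/days) × (days/union days) = units/union days, the current formula. In the Step 1 offset case, 2 × 110 × 180/270 = 146.7.
- Unweighted sum of class doses: 200 units/day of premix for 135 days, then 100 basal + 100 bolus for 135 days, gives 200 + 100 + 100 = 400, although the dose was 200 throughout.
- Weighting by time in use, with gaps of up to 30 days bridged and edges included: the offset case gives 110 × 270/270 × 2 = 220. The sequential case gives (200 + 100 + 100) × 135/270 = 200. U-500R gives 220.

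**The case against.** **Purchased dose and compliance.** Section 3 says that claims show insulin purchased, not taken or prescribed, and Section 6.4.1 says that a change in TDD may reflect compliance. A day with basal but no bolus in supply may be real under-dosing, so part of the pre-index fall may be signal. A reader might infer that the whole rise is artefact; the documents do not support that. The comparison is still unequal, because a lapse in U-500R is dropped from TDD while a lapse in one of two classes lowers it.

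**ADD is already planned.** Section 3 undertakes to compare PDC, TDD and ADD together, and at equal purchasing ADD stays flat, so a rise in TDD alone would be visible descriptively. That stands for the description. It does not help the entry test, the covariate or the mediator.

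**Selection limits the size.** An admitted patient on an unchanged dose D cannot show a false rise of D − 180 or more, so at D = 200 it is under 20 units/day. A given patient is either excluded or distorted, not both. This bounds the bias for lower doses but does not remove it.

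**Not everyone is affected.** Entry requires only one claim for another insulin, and the basal-bolus statement in Section 3 is an expectation, not a criterion. Patients on one class are unaffected.

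**Post-index TDD can also fall.** A reader might infer that nothing lowers it. That holds only for refill timing of one product. If concurrent vial and Kwikpen days were added without adjustment, 6,600 units over 60 days would give 110 instead of 220. That is a separate question.

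**Conclusion.** The point holds as a lack of comparability fixed in the protocol's own definition. For patients on two or more classes before the index, TDD is diluted by single-class days, while refill gaps on U-500R cancel. With unchanged dosing and refilling, change in TDD is biased upward and >180 is a stricter test before the index.

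The size is not known from the documents. The 5%, 10% and 20% figures rest on two equal classes, independent filling, assumed coverage of 0.95, 0.9 or 0.8, and the union reading of the overlap note. The bias is zero where coverage coincides or one class was used.

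A reader might infer that the formula explains much of the increase reported from the earlier Kwikpen study ("The insulin dose increased more than 80 units/day"). The documents do not support this. They do not give that study's TDD formula or its coverage per class, and its cohort was not restricted to >180. For the same reason, the mean doses quoted in Section 3 should not be used to size the bias here.

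**What to change.** Reword the TDD row of Table 2:
- For each insulin class (basal, bolus, premixed, U-500R), compute units divided by days of supply.
- Multiply by the share of insulin-treated time the class was in use, and sum over classes.
- Define in use as first fill to last run-out, bridging gaps, including those at the period edges, up to a pre-specified length. Do not define it as days in supply, which reproduces the present formula.
- Apply this TDD in both periods to change in TDD, the >180 and >2000 tests, the covariate and the mediator.
- Keep the union-of-days TDD as a sensitivity analysis, reported beside ADD.

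The cost is one added assumption (the gap length), reprogramming of one derived variable from the same claims, and less comparability with the earlier full-cohort study. The assumption matters: in the offset example a bridge shorter than 30 days gives 146.7 again, and leaving the edges unbridged gives 2 × 110 × 240/270 = 195.6. The length should therefore be fixed before the data are seen and varied in a sensitivity analysis. Some patients near 180 will enter or leave the cohort.

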Currently, the treatment patterns, compliance, and outcomes with U-500R among those who did not utilize U-500R consistent with the FDA label in the real-world setting is unknown. Neither is the treatment patterns, adherence behavior, and outcomes among those who did utilize U-500R in the manner that was consistent with FDA label. All previous real-world evidence (RWE) studies have studied all available U-500R patients (full RWE cohort) without distinguishing the manner that U-500R was utilized although more recent studies revealed a significant amount of off-label use. Therefore, as part of a series of studies for U-500R, the aim of this study is to examine the treatment patterns, compliance, effectiveness and safety outcomes among those utilizing U-500R consistently with the FDA label (high-dose cohort). Another study will be conducted in parallel to understand those who did not utilize U-500R consistently with the FDA label (Lower-dose cohort). Prior to any analysis, it is necessary to capture the real-world definition for the high-dose population based on the prescribing pattern and insulin titration consideration. In a clinical trial conducted by Hood et al, a reduction of dose up to 20% in the first U-500R insulin dose was recommended, and to keep patients at target the dose of insulin was titrated to a target with a -10% to +15% dose change with all insulins. At the end of the study, 2.3% of patients were taking ≤ 150 units of insulin and 11.2% were on ≤ 200 units of insulin.¹⁵ Similar treat to target algorithms were also used in another clinical trial conducted by Grunberger et al.¹⁶ Given these attributes, a 10% reduction of recommended dose of U-500 insulin (>180 units) is justifiable to define the high-dose cohort. Additionally, in a large ongoing real-world study evaluating the treatment patterns among U-500R initiators, U-500R syringe initiators and U-500R Kwikpen initiators had a mean TDD of 198 ± 78 units (median: 189 units) and 188 ± 72 units (median: 176 units), respectively. This data suggest that exclusion of patients receiving a TDD of <180 units in both U-500R syringe and Kwikpen cohorts (which consists of $>25\%$ of all observed patient data) would most likely yield an aggregate median and mean $TDD > 200$ units of insulin which is consistent with Humulin R-U500

[2019-8636] Observational Study Protocol

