Concomitant medications ^{28,29,30}	Truven: Outpatient pharmacy claims table VHA: Pharmacy file	A flag will be created for patients prescribed the following antihyperglycemic agents (AHA):

[2019-8636] Observational Study Protocol

Variable	Source	Definition
		thiazolidinediones, sulfonylureas, biguanides, meglitinides, alpha-glucosidase inhibitors, DPP-4 inhibitors, SGLT-2 inhibitors, bile acid sequestrants, fixed-dose combinations, GLP-1 receptor agonists, and amylin agonists (Appendix 1).
HbA1c ³¹	VHA: Lab file	The HbA1c value in the pre-index and post-index period for each index event will be reported. Pre-index HbA1c will be the HbA1c measurement -90/+30 days of the index date. For patients with multiple HbA1c measurements within this period, the measurement taken closest to the index event date will be reported as the pre-index HbA1c value. The post-index HbA1c value will be the farthest HbA1c measurement taken in the time period after the 30 day-post index event date.
Change in HbA1c		The change in HbA1c will be defined as the difference in the pre-index and post-index HbA1c values.
Hypoglycemic events	Truven: Inpatient service table, outpatient service table VHA: Inpatient and outpatient files, Lab file and Pharmacy file	Hypoglycemia events in the pre- and post-index periods will be evaluated using the ICD-9 codes from the Ginde algorithm (Appendix 1), ³² the presence of a cutoff of blood glucose ≤ 70 mg/dL, or any evidence of intramuscular glucagon administration (Appendix 1). Hypoglycemia events that occurred on or after the index date will be considered the follow-up hypoglycemia event; and hypoglycemia event occurred on or prior to - 1 day of the index date will be considered as the pre-index hypoglycemia event. The number of hypoglycaemia events per patient per year (PPPY) will be reported in both the pre-and post-index periods.

[2019-8636] Observational Study Protocol

Variable	Source	Definition

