- ❖ Age, sex, race, BMI, and CCI score will be assessed during pre-index period. Adherence (PDC) and observed TDD will be calculated during the entire pre-index and post-index periods, respectively.
- ❖ The abovementioned statistical approach for Primary Objective 1 will be repeated in the subgroup analyses for elderly population and other subgroup high-dose cohorts (i.e., TDD =201-300 units and TDD >300 units [optional]).

[2019-8636] Observational Study Protocol**Research Objective 2: Primary Objective 2**Descriptive Analysis

HbA1c will be analyzed descriptively before and after high-dose U-500R Kwikpen initiation, high-dose U-500R syringe initiation, and before and after any high-dose U-500R initiation.

Numbers and percentages will be provided for dichotomous and polychotomous variables. Means and SDs will be provided for continuous variables. McNemar's test will be used to determine statistical significance of before and after values for categorical variables, and the paired t-test will be used to assess the statistical significance of before and after values in continuous variables.

Multivariate Analysis: HbA1cMixed Linear Model

A mixed linear model (see details above) will be used to evaluate factors associated with HbA1c level in the pre-and post-index periods among high-dose U-500R Kwikpen initiators, high-dose U-500R syringe initiators, and any high-dose U-500R initiators. For this objective, the mixed linear model will help to evaluate the effect of both time-varying and time-independent variables on the HbA1c, while taking into account for correlation due to multiple assessments from the same individual. In the current model, HbA1c level, (measured at 2 time intervals [before and after the index event: U-500R initiation]), will be considered the dependent variable. Observed TDD will be designated as the time-varying covariate in the model (measured both before and after the index event), and the time-independent covariates include the demographic and clinical characteristics.

The complete list of covariates will include:

- age;
- sex;
- race;
- BMI;
- Pre-index CCI score;
- observed TDD from claims; and
- time (pre/post).

Note:

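### Primary Objective 2 compares one HbA1c near the first U-500R fill with one later value and has no earlier value or comparator, so it cannot separate a U-500R effect from regression to the mean or pre-switch worsening

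*Protocol*

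**What the plan says.** Protocol Section 5.5, Table 2, sets the baseline window: "Pre-index HbA1c will be the HbA1c measurement -90/+30 days of the index date". When several values fall in it, "the measurement taken closest to the index event date will be reported as the pre-index HbA1c value". The outcome is also a single value: "The post-index HbA1c value will be the farthest HbA1c measurement taken in the time period after the 30 day-post index event date". Change is the raw difference: "The change in HbA1c will be defined as the difference in the pre-index and post-index HbA1c values".

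Section 6.4.1 (Primary Objective 2) tests this with a paired t-test and a mixed linear model in which the outcome is "HbA1c level, (measured at 2 time intervals [before and after the index event: U-500R initiation". The covariates are introduced with "The complete list of covariates will include" and are age, sex, race, BMI, pre-index CCI, observed TDD and the pre/post time term. The list has no earlier HbA1c and no pre-index slope, and the design has no comparator group.

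Section 3 states the aim as to "examine the treatment patterns, compliance, effectiveness and safety outcomes among those utilizing U-500R consistently with the FDA label". The data limitations in Section 5.2 mention neither regression to the mean nor a trend before initiation.

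**The concern.** Without a comparator, the pre-index HbA1c is the only reference for what would have happened without U-500R. A value close to a treatment change may be one of the values that led to it. If so, it is on average high for that group of patients, and part of the later fall would occur without any treatment effect. If HbA1c was also worsening temporarily before the switch, more of the fall would be recovery. Two values per patient cannot reveal either.

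The protocol makes this plausible. Section 3 describes U-500R as a product for improving glycaemic control, says that targets are hard to reach on U-100, links individual dosing to glucose level and treatment goal, and cites evidence of too little insulin use before the switch. For out-of-pocket costs, Section 3 warns that the pre-index figure may be distorted, and Section 6.4.1 plans adjustment and a mediation analysis. HbA1c, a primary objective, has no matching safeguard. At stake is whether a before/after fall can be read as effectiveness.

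**Working it through.** The protocol gives no power calculation and no HbA1c mean, SD, correlation or trend, so there is no figure to reproduce. The calculations below are illustrations.

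**Inputs from the protocol.** Preliminary VHA counts are 647 (Kwikpen) and 1,766 (syringe) in Section 6.1, Table 3. Tests are two-sided at 0.05 (Section 6.3). **Assumed inputs.** HbA1c SD is 1.5, the correlation rho between two HbA1c values of one patient is 0.4 to 0.8, and the selected group's baseline mean exceeds the source-population mean by 0.25 to 1.0 points.

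**Step 1, regression to the mean.** Expected fall without treatment effect = (1 - rho) x excess.

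| Assumed excess | rho 0.4 | rho 0.6 | rho 0.8 |
|---|---|---|---|
| 0.25 | 0.15 | 0.10 | 0.05 |
| 0.5 | 0.30 | 0.20 | 0.10 |
| 1.0 | 0.60 | 0.40 | 0.20 |

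The excess is measured from the source-population mean. A transient excess over a patient's own usual level would be expected to disappear in full, so the factor (1 - rho) does not apply to it.

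**Step 2, what the paired test would call significant.** SE = SD x sqrt(2(1 - rho)/n).
- n = 647, rho 0.8: 1.5 x sqrt(0.4/647) = 0.037, threshold 1.96 x 0.037 = 0.073. At rho 0.4 the threshold is 0.127.
- n = 1,766: thresholds 0.044 (rho 0.8) and 0.077 (rho 0.4).
- With zero true effect and the Step 1 values, the probability of p < 0.05 runs from 27% to about 100% at n = 647, and from 60% to about 100% at n = 1,766.
- A fall of 0.06 at rho 0.8 and n = 647 gives z = 0.06/0.037, about 1.6, which is not significant.
- Table 3 does not name the TDD >180 or monotherapy criteria, so final cohorts may be smaller. At an assumed n = 250 and rho 0.6, the threshold is 1.96 x 1.5 x sqrt(0.8/250) = 0.17.

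**Step 3, would an earlier value help?** Three equally correlated values (early, near-index, post; mean 8.5, SD 1.5) were simulated with no treatment effect. The log-odds of starting U-500R rose by 0.25 to 1.0 per HbA1c point at the near-index value. The planned near-index to post change was -0.10 (rho 0.8, log-odds 0.25) to -0.99 (rho 0.4, log-odds 1.0). The early to post change stayed within 0.02 of zero. With log-odds 0, both changes were about zero.

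This result depends on equal correlations. If the early value correlates more closely with the near-index value than the post value does, a residual of excess x (difference in rho) remains, for example 0.5 x (0.8 - 0.6) = 0.10. The early contrast is therefore a check and not a full correction.

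**Step 4, are early values within reach?** Section 5.3.1 requires 9 months of enrolment before the index date. VHA data start on 01APR2013, nine months before the first possible index date of 01JAN2014 (Section 5.4). Days -270 to -91 are thus inside the data window for every VHA patient, although a measurement need not exist.

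**The case against.** The strongest counter-case has five parts.

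1. The index date is the first fill, not the decision, and the window runs to day +30. A value taken after the first fill cannot have prompted the switch and would shrink a true fall. This stands. A reader might infer that the bias runs only in favour of U-500R, but the document does not support that.
2. Entry requires an HbA1c measurement, not an HbA1c level (Section 5.3.1), and Section 3 gives other reasons for choosing U-500R, such as smaller volume and pen convenience. This stands: selection on high HbA1c is plausible but not shown, and without it Step 3 finds no artefact.
3. The objectives ask for differences and associated factors, and the time coefficient is adjusted for observed TDD, so it is not the total change. This is true, but the stated aim speaks of effectiveness and nothing warns the reader against that interpretation.
4. HbA1c may have been rising persistently, with U-500R reversing only the recent rise. The near-index value is then the fairer reference, so requiring the post value to fall below the early one before concluding effectiveness would be too strict. This stands.
5. An unseen SAP may hold a sensitivity analysis. However, the protocol itself fixes two values per patient and a covariate list that it calls complete.

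**Conclusion.** The point holds as a limit on interpretation. As specified, the paired difference and the time coefficient cannot tell a U-500R effect from regression to the mean or pre-switch worsening, and the protocol plans no earlier value, trend check or caveat. This matters only if initiation responds to HbA1c.

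Under the assumptions above, regression to the mean would be 0.05 to 0.60 points, which can reach significance at the preliminary counts but need not. A reader might go further and express the artefact as a share of the roughly 0.7-point drop cited in Section 3. The document does not allow this: to explain all of it, the excess would have to be 0.7/0.6 = 1.17, 0.7/0.4 = 1.75 or 0.7/0.2 = 3.5 points at rho 0.4, 0.6 or 0.8, and nothing in the protocol shows which excess or rho applies. The cited drop is also an adjusted Kwikpen result from a study not restricted to the high-dose cohort. Neither the size nor the net direction of the bias can be fixed from the document.

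**What to change.** In Section 6.4.1, add a third HbA1c time level to the Primary Objective 2 mixed model: the value nearest day -180 within days -270 to -91, from the VHA lab file. Keep patients who lack it; they still contribute their two planned values.

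Report near-pre versus early-pre and post versus early-pre beside the planned contrast. Give each with and without observed TDD, because TDD is one figure for the whole pre-index period and both pre-index levels would share it. Tabulate how many baseline values date from after the first fill.

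State two limitations. A before/after fall is not attributed to U-500R where near-pre exceeds early-pre and post does not differ from early-pre, judged on estimates and confidence intervals. The early-pre contrast may understate benefit if HbA1c was persistently rising.

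The cost is one further time level from a lab file already in use, with no change to entry criteria. The early contrast will rest on fewer patients, by an unknown number: requiring pre- and post-index HbA1c already takes Table 3 from 2,536 to 741 (Kwikpen) and from 4,956 to 1,930 (syringe). The headline change may look smaller.
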